## 3.5.1. Adverse Events

An adverse event is considered treatment-emergent relative to study intervention if the adverse event start date is during the on-treatment period (including on the date of first dose).

AEs will be as characterized by type, severity, timing, seriousness, and relationship to study intervention.

AEs (except CRS and ICANS) will be graded by the investigator according to the NCI CTCAE version 5.0. CRS and ICANS will be graded by the investigator according to the ASTCT criteria. All AEs will be coded using the most current version of Medical Dictionary for Regulatory Activities (MedDRA).

TEAEs leading to dose interruption or dose reduction will be derived from the exposure CRF (dose adjustment reason as adverse event and actual dose taken of 0 for interruption and >0 for reduction) and then linked programmatically to the adverse event CRF by the AE identifier.

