6.4. Study Intervention Compliance

Participants will receive study intervention directly from the investigator or designee, under medical supervision. The date and time of each dose administered in the clinic will be recorded in the source documents and recorded in the CRF. The dose of study intervention and study participant identification will be confirmed at the time of dosing by a member of the study site staff other than the person administering the study intervention.

The site will complete the required dosage Preparation Record located in the IP manual. The use of the Preparation Record is preferred, but it does not preclude the use of an existing appropriate clinical site documentation system. The existing clinical site's documentation system should capture all pertinent/required information on the preparation and administration of the dose. This may be used in place of the Preparation Record after approval from the sponsor and/or designee.

Compliance with study intervention will be documented in the source documents and CRF. Study intervention start dates, reasons for delays, dose reductions, and/or missed doses will be recorded in the CRF. Deviation(s) from the prescribed dosage regimen will be recorded in the CRF.

A record of study intervention dispensed to and administered to each participant must be maintained.

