6.6.1. Redosing criteria

During a cycle: Re-treatment following interruption for treatment-related toxicity and for peripheral neuropathy (any causality) within a cycle should follow the dose modification and guidance section below (Section 6.6.2).

Participants must receive both elranatamab priming doses before receiving the planned full dose (76 mg). If the C1D4 dose (32 mg) cannot be administered within the protocol-defined window, elranatamab treatment may resume at the planned C1D4 dose (32 mg) upon meeting the re-treatment criteria. Upon re-treatment, if the C1D4 dose (32 mg) was tolerable, the elranatamab dose should be increased to the planned full dose (76 mg) approximately 4 days later, after which QW dosing with the planned full dose (76 mg) should continue **CC**

Dose reductions, as outlined in Section 6.6.2 (Table 2), are only applicable after the first full planned dose (76 mg) is administered.

At the start of a cycle: Re-treatment at the start of any new cycle should not occur until all of the following parameters have been met:

- ANC $\geq 1.0 \times 10^9/L$
- Platelet count $\geq 25 \times 10^9/L$
- Recovery of treatment-related nonhematologic toxicities to baseline or Grade ≤1 severity.
- For any dosing day (at start of a cycle or during a cycle [Section 6.6.2]), no ongoing CRS or ICANS (any grade)
- Recovery of treatment-emergent peripheral neuropathy to Grade ≤ 1 severity.

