a. Dose reduction guidance is not applicable following the first and second doses (priming doses C1D1 and C1D4). If after the C1D4 priming dose, a participant experiences a treatment-related adverse event that leads to dose interruption (ie, dose held on Cycle 1 Day 8), elranatamab treatment may restart at the same dose (32)

Table 2.Dose Modifications for Elranatamab-Related Toxicity and for Peripheral
Sensory or Motor Neuropathy a

mg) upon meeting the redosing criteria (Section 6.6.1). If the 32 mg dose was tolerable, the elranatamab dose should be increased to 76 mg. In case of ongoing CRS or ICANS of any grade on any dosing day, dosing will be held until resolution.

b. Grade 3 or 4 nausea, vomiting or diarrhea must persist at Grade 3 or 4 despite maximal medical therapy to require dose modification or permanent discontinuation.

c. Excludes lymphopenia which is expected based on the elranatamab mechanism of action.

d. For thrombocytopenia: dosing can continue if platelets $\ge 25 \times 109/L$. For Grade 4 (first occurrence), resume at same dose level when platelets $\ge 25 \times 109/L$; for Grade 4 (second occurrence), resumption at a reduced dose level is recommended when platelets $\ge 25 \times 109/L$.

- e. Consider additional diagnostic work-up (see Section 8.3.11)
- f. Excludes laboratory abnormalities that are not considered clinically relevant.

Note: Cycles will not be extended to allow make-up for missed doses.

Doses may be held as needed until toxicity resolution. Appropriate follow-up assessments should be done until adequate recovery occurs as assessed by the investigator.

Missed doses will not be made up and cycles will not be extended to allow for missed doses. A minimum of 2 days should be maintained between the 2 step-up doses (C1D1 and C1D4), a minimum of 3 days between C1D4 dose and the first full dose (C1D8); a minimum of 6 days is required between doses thereafter.

C1D1 will be based on Day 1 of elranatamab dosing. After C1D1, for each cycle, if elranatamab cannot be administered on the planned day (within the window prespecified in the SoA), it should be skipped until the next planned dose (ie, if Day 15 cannot be administered within ± 3 days of planned dose, the dose should be skipped until Day 22).

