#### 6.6.3.1. Dose Reductions, Interruptions, and Delays

A dose reduction is defined as a nonzero dose that is less than the planned and previous non-zero dose. The planned dose is the same as the prior dose except for C1D4 and C1D8.

The number and percentage of participants with at least 1 dose reduction as well as a breakdown of dose reductions  $(1/2/3/ \ge 4)$  will be summarized by cohort. In addition, the number and percentage of participants with at least 1 dose reduction due to AE will also be summarized.

An interruption is defined as a continuous missed scheduled dose based on the planned dosing frequency (QW or Q2W). The number and percentage of participants with dose interruptions as well as a breakdown of dose interruptions  $(1/2/3/\geq 4)$  will be summarized by cohort and overall. In addition, the number and percentage of participants with at least 1 dose interruption due to AE will also be summarized. Percentages will be calculated based on the total number of participants in the Safety Analysis Set.

A dose delay will be derived based on study drug administration date and will be grouped into the following categories based on the deviation of the actual to the planned treatment administration day (relative to the previous treatment administration date):

- No delay;
- 1-3 days delay;
- 4-6 days delay;
- 7 or more days delay (only in the Q2W schedule).

The number and percentage of participants with delayed study drug administration and maximum length of delay, ie, the worst case of delay if participants have multiple dose delays will be summarized by cohort, as applicable.

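### SAP 3.5.1 classes an AE as leading to dose reduction without testing that the dose fell, so it can disagree with the definition of a reduction in SAP 6.6.3.1

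*SAP*

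**What the plan says.** **AE tables.** SAP 3.5.1 takes AEs leading to interruption or reduction from the exposure CRF, on the basis of "dose adjustment reason as adverse event and actual dose taken of 0 for interruption and >0 for reduction", and links them to the AE page by the AE identifier. It does not refer to SAP 6.6.3.1. The derivation supplies the dose-reduction rows in the AE overview and the SOC/PT summaries (SAP 6.7.1), the AESI tables (SAP 6.7.1.1) and the tables for other AEs of clinical interest (SAP 6.7.1.2).

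**Exposure table.** SAP 6.6.3.1 sets its own test: "A dose reduction is defined as a nonzero dose that is less than the planned and previous non-zero dose". It adds: "The planned dose is the same as the prior dose except for C1D4 and C1D8". From this it produces a second AE-related output: "the number and percentage of participants with at least 1 dose reduction due to AE will also be summarized".

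**Protocol.** Section 6.6.1 states: "Dose reductions, as outlined in Section 6.6.2 (Table 2), are only applicable after the first full planned dose (76 mg) is administered". Footnote a to Table 2 (Section 6.6.2) covers a treatment-related AE after the C1D4 dose that causes the C1D8 dose to be held. In that case "elranatamab treatment may restart at the same dose (32" mg), once the redosing criteria are met. On data capture, Section 6.4 says only that "reasons for delays, dose reductions, and/or missed doses will be recorded in the CRF".

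**The concern.** One SAP applies two tests to the same term. The SAP 3.5.1 test asks whether there was an AE reason and whether any drug was given. The SAP 6.6.3.1 test asks whether the dose went down. A non-zero dose that is unchanged from the one before can pass the first and fail the second.

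The case that separates them is not exotic. The protocol itself allows 32 mg to be given again after an AE hold at C1D8. That happens in the priming phase, when CRS and ICANS are the main concern and when the protocol says its dose-reduction guidance does not yet apply.

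At stake is whether the safety tables agree with each other. One report could give two different counts under nearly the same label. The AESI tables could also show CRS or ICANS leading to a dose reduction in a participant whose dose was never lowered.

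**Working it through.** There is no planned figure to reproduce. The check applies each rule to the same dosing records.

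**Rules**

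- SAP 3.5.1: reduction if the reason is AE and actual dose > 0; interruption if the reason is AE and actual dose = 0.
- SAP 6.6.3.1: reduction if actual dose > 0, actual < planned, and actual < previous non-zero dose.

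**Dose inputs.** Protocol Table 3 gives levels of 76, 44 and 32 mg, with 12 mg for C1D1 only. Under SAP 6.6.3.1 the planned dose equals the prior dose except at C1D4 (32 mg) and C1D8 (76 mg).

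**Results.** Every record below is assumed to carry an AE adjustment reason, except the last.

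| Record | Previous non-zero (mg) | Actual (mg) | SAP 3.5.1 | SAP 6.6.3.1 |
|---|---|---|---|---|
| C1D8 held | 32 | 0 | interruption | interruption |
| 32 mg repeated, entered at the C1D8 visit (planned 76) | 32 | 32 | reduction | not a reduction |
| 32 mg repeated at a later visit (planned 32, or 76 by schedule) | 32 | 32 | reduction | not a reduction |
| 76 lowered to 44 | 76 | 44 | reduction | reduction |
| 44 lowered to 32 | 44 | 32 | reduction | reduction |
| 32 mg repeated, no AE reason on that record | 32 | 32 | neither | not a reduction |

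For the repeat, 32 > 0 satisfies SAP 3.5.1. Under SAP 6.6.3.1, 32 < 32 is false, so the record fails whether the planned dose is read as 32 or 76. The two rules agree on genuine reductions and on held doses. In this table they differ only where an unchanged non-zero dose carries an AE reason.

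**Size per participant.** Protocol 9.2 gives 123 treated in Cohort A and 64 in Cohort B; 123 + 64 = 187, matching Protocol 2.2.3.2.

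- Cohort A: 1/123 = 0.8 percentage points
- Cohort B: 1/64 = 1.6 percentage points
- Overall: 1/187 = 0.5 percentage points

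The effect is proportional to the number of participants affected. The documents do not give that number.

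**After adding the SAP 6.6.3.1 condition to SAP 3.5.1.** The repeated 32 mg is no longer a reduction. The steps from 76 to 44 and from 44 to 32 still count, and 0 mg records remain interruptions.

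**The case against.** The strongest reply is that the miscount depends on a CRF that is not in the documents. SAP 3.5.1 acts only where the record itself gives AE as the adjustment reason. Footnote a calls the repeat a restart at the same dose, so a site might enter the AE reason only on the 0 mg hold record. SAP 3.5.1 would class that correctly as an interruption and would not count the repeat at all. If the repeat falls at a later visit, SAP 6.6.3.1 makes the planned dose 32 mg, and there may be no adjustment to explain. This stands. It makes the miscount conditional, but it does not remove the difference between the rules.

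The pathway may also be uncommon. The footnote permits a restart at 32 mg, while other passages (for example Protocol 6.1.1) speak only of deferring the dose. Protocol 4.3 reports CRS after the second dose in 2 of 50 Phase 1 SC participants, under different dosing. This too stands, and it is a reason not to put a rate on the problem.

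Nor are all rows exposed. Where the C1D8 hold is recorded as 0 mg with an AE reason, the participant already counts in the combined row for interruptions or reductions. Only the separate reduction rows would then differ.

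Four stronger readings are tempting, and the documents support none of them:

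- **That repeated priming doses will be reported as reductions.** This holds only if the non-zero record carries the AE reason.
- **That a full 76 mg dose given late because of an AE is also counted.** This needs delay reasons to share the dose-adjustment field. Protocol 6.4 says only that they are recorded, and SAP 6.6.3.1 derives delays from administration dates.
- **That reported reduction rates will be inflated by several percentage points.** No count or rate of such records is given.
- **That the protocol itself classifies the repeat as not a reduction.** Sections 6.6.1 and 6.6.2 say when reduction guidance applies and call the repeat the same dose. They do not set a rule for classifying exposure records in tables.

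**Conclusion.** Wrong as written, minor. As stated, the SAP 3.5.1 rule can label an unchanged dose as a reduction, and it conflicts with the definition the same SAP gives in 6.6.3.1. On a repeated 32 mg dose with an AE adjustment reason, the AE, AESI and other-AE-of-interest tables would count a reduction that the exposure table does not.

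The divergence of the rules follows from the text alone. Whether any participant is affected rests on one assumption: that the AE reason is entered on the non-zero record. The per-participant sizes shown above are therefore a scale, not an estimate of the error. The primary endpoint, the hypothesis tests and the error rates are untouched.

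**What to change.** Reconcile the two SAP passages. In SAP 3.5.1, class an AE as leading to dose reduction only when the exposure record gives AE as the adjustment reason and the dose meets the SAP 6.6.3.1 definition, that is, non-zero and below both the planned and the previous non-zero dose. Leave 0 mg records with an AE reason as interruptions.

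This also makes the dose-reduction rows independent of which record a site attaches the AE reason to when 32 mg is repeated. Extra rows for repeated priming doses or for delays are a matter of preference and are not needed to remove the conflict.

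The cost is one sentence in the SAP and one condition in the derivation. No new data are needed, and no dosing rule changes.

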### **3.5.2.** Laboratory Data

Hematology and chemistry results will be programmatically graded according to the NCI CTCAE version 5.0 for relevant parameters. A shift summary of baseline grade by maximum postbaseline grade will be presented. Parameters which cannot be graded will be summarized relative to the normal range (ie, normal range high or normal range low). Additional details are provided in Section 6.7.3.

## 4. ANALYSIS SETS (POPULATIONS FOR ANALYSIS)

For purposes of analysis, the following analysis sets are defined:

Defined Analysis Set	Description
Safety Analysis Set	The safety analysis set in each cohort will include all enrolled participants in the respective cohort who received at least one dose of study intervention. This will be the primary analysis population for evaluating participant characteristics, treatment administration/compliance and safety endpoints.
Final Analysis Evaluable Set	The final analysis evaluable set in each cohort will include all enrolled participants in the respective cohort who received at least one dose of study intervention. This will be the primary analysis population for evaluating efficacy endpoints. This is the same as the safety analysis set thus only the "safety analysis set" terminology will be used.
Interim Analysis Evaluable Set A	The interim analysis evaluable analysis set A will include the first 90 enrolled participants who received at least one dose of study intervention in Cohort A. This will be the primary analysis population for evaluating efficacy endpoints at the interim analysis for Cohort A.

Interim Analysis Evaluable Set B	The interim analysis evaluable analysis set B will include the first 30 enrolled participants who received at least one dose of study intervention in Cohort B. This will be the primary analysis population for evaluating efficacy endpoints at the interim analysis for Cohort B.
PK Analysis Set	The PK analysis set is a subset of the safety analysis set and will include participants who have at least one postdose concentration measurement.
Immunogenicity Analysis Set	The immunogenicity analysis set is a subset of the safety analysis set and will include participants who have at least one sample tested for ADA.
Biomarker Analysis Set	The biomarker parameter analysis set in each cohort is a subset of the safety analysis set and will include participants who have at least one baseline biomarker assessment.
	Analysis sets will be defined separately for biomarkers based on blood, saliva, and bone marrow samples.
PRO Analysis Set	The PRO analysis set in each cohort will include all participants in the safety analysis set who completed a baseline (last PRO assessment prior to or on the first dose of study intervention) and at least one post-baseline PRO assessment.
Note : "Enrolled" means a participation of the informed consent process and the informed consent p	ant's agreement to participate in a clinical study following completion of was assigned to treatment. Potential participants who are screeped for the

*Note:* "Enrolled" means a participant's agreement to participate in a clinical study following completion of the informed consent process and was assigned to treatment. Potential participants who are screened for the purpose of determining eligibility for the study, but do not participate in the study, are not considered enrolled, unless otherwise specified by the protocol.

## 5. GENERAL METHODOLOGY AND CONVENTIONS

## 5.1. Hypotheses and Decision Rules

#### 5.1.1. Hypotheses and Sample Size

This study has two cohorts: Cohort A will enroll participants who are naïve to BCMA-directed therapies, and Cohort B will enroll participants who have prior exposure to BCMA-directed therapies. The primary objective of this study is to determine the efficacy in Cohort A and Cohort B with respect to ORR by BICR, as defined by IMWG.

In Cohort A, the study will test the null hypothesis that the ORR by BICR as defined by IMWG is  $\leq$ 30% versus the alternative hypothesis that the ORR by BICR as defined by IMWG is >30%. In Cohort B, the study will test the null hypothesis that the ORR by BICR as defined by IMWG is  $\leq$ 15% versus the alternative hypothesis that the ORR by BICR as defined by IMWG is >15%.

The sample size for Cohort A and Cohort B was calculated to provide adequate power for testing the statistical hypotheses regarding the primary endpoint of ORR independently in the two cohorts using a two-stage design based on exact binomial distribution. A total of 120 participants enrolled and treated in Cohort A provides approximately 98% power to detect a true ORR by BICR of 48% to reject the null hypothesis, with a 1-sided significance level of 0.025. Similarly, a total of 60 participants enrolled and treated in Cohort B provides

approximately 91% power to detect a true ORR by BICR of 34% to reject the null hypothesis, with a 1-sided significance level of 0.025.

At the time of the SAP amendment, 31% of Cohort A had EMD at baseline. If the null hypothesis for ORR by BICR is rejected for Cohort A, the key secondary endpoint of ORR by BICR for those without EMD at baseline will be tested in a hierarchical fashion using the gatekeeping procedure that the ORR is  $\leq$ 38% with a 1-sided significance level of 0.025. If the null hypothesis for ORR by BICR for those without EMD at baseline is rejected for Cohort A, the key secondary endpoint of ORR by BICR for those with EMD at baseline is rejected for Cohort A, the key secondary endpoint of ORR by BICR for those with EMD at baseline will be tested in a hierarchical fashion using the gatekeeping procedure that the ORR is  $\leq$ 12% with a 1-sided significance level of 0.025.

An interim analysis for both futility (non-binding) and efficacy will be conducted on ORR by BICR for Cohort A based on the first 90 participants enrolled and treated in that cohort, and for Cohort B based on the first 30 participants enrolled and treated in that cohort. Each respective interim analysis will occur no earlier than the point at which all early responders (ie, those who respond within the first 3 post-baseline assessments) among the participants to be included have had their responses confirmed.

## 5.1.2. Decision Rules

An interim analysis for both futility (non-binding) and efficacy will be conducted for the primary endpoint for Cohort A and Cohort B. At the time of the interim analysis, the testing rule based on an exact binomial test will depend on the actual number of participants included in the analysis for each cohort with sufficient follow-up.

At the time of the SAP amendment, enrollment had exceeded the 120 Cohort A and 60 Cohort B participants. At the time of the final analysis, the testing rule based on an exact binomial test will depend on the exact number of participants enrolled and treated in each cohort, respectively. Operating characteristics (Type I and Type II error) were calculated using the exact binomial distribution based on the current enrollment (see below). It can be noted that the futility and efficacy stopping boundaries for both cohorts at the interim analysis are equivalent to what would be induced if using the rho family beta-spending boundary with parameter = 3 and the rho family alpha-spending boundary with an exact binomial test.

At the interim analysis for each cohort, accrual may be stopped for further evaluation due to futility; otherwise, the cohort will proceed as planned to the final analysis, and all ongoing participants will continue with scheduled visits per the schedule of activities in the protocol.

At the time of the SAP amendment, 94 Cohort A participants were initially dosed at least 4 months prior to the data cutoff and will be included in the interim analysis. The interim analysis will include a few participants with EMD at baseline who have insufficient follow-up for confirmed response. No interim analysis will be performed for Cohort B participants as not enough participants have adequate follow-up since Cohort B has a higher incidence of EMD at baseline compared to Cohort A. The boundaries at the final analysis for Cohort B do not change if no interim analysis is performed.

Cohort A: Operating Characteristics								
	Futility Criteria (responders/patients)	Efficacy Criteria (responders/patients)	Cumulative alpha spent*	Cumulative beta spent**				
Interim Analysis	≤33/94	≥41/94	0.0036	0.0078				
Final Analysis	≤47/123	≥48/123	0.0207	0.0204				

\* Cumulative alpha spent calculated assuming the null ORR of 0.30.

\*\* Cumulative beta spent calculated assuming the target ORR of 0.48.

Cohort B: Operating Characteristics							
	Futility Criteria	Efficacy Criteria	Cumulative	Cumulative beta			
	(responders/patients)	(responders/patients)	alpha spent*	spent**			
Interim Analysis	≤3/30	≥13/30	0.0002	0.0027			
Final Analysis	≤15/64	≥16/64	0.0248	0.0471			

\* Cumulative alpha spent calculated assuming the null ORR of 0.15.

\*\* Cumulative beta spent calculated assuming the target ORR of 0.34.

The final analysis of each cohort will be conducted once all participants have had at least 2 post-baseline response assessments or have otherwise discontinued response assessments within the first 2 months of treatment.

